4.2 SECONDARY EFFICACY VARIABLES

The following secondary efficacy variables will be analysed:

4.2.1 Main Secondary Efficacy Endpoint

Proportion of patients achieving a categorical ACR20 response at Week 12.

The components of ACR20 assessment include:

- C-Reactive Protein (CRP) (mg/L),
- Tender/painful joint count (TJC) (28 joints),
- Swollen joint count (SJC) (28 joints),
- Patient assessment of joint pain (Pain-VAS),
- Patient global assessment of disease (PtGA),

- Physician's Global Assessment of Disease (PrGA),
- HAQ-DI

4.2.2 Other secondary endpoints

- Change from Baseline in the following disease parameters at Week 2, Week 4, Week 8 and Week 12:
 - Individual components of the ACR20 response (CRP, TJC(28), SJC(28), Pain-VAS, PtGA, PrGA, HAQ-DI)
 - Erythrocyte Sedimentation Rate (ESR);
 - DAS28-CRP and DAS28-ESR. The components of DAS28 assessment include TJC(28), SJC(28), CRP/ESR, and PtGA;
 - SDAI score which includes TJC(28), SJC(28), CRP, PtGA, and PrGA;
 - CDAI score which includes TJC(28), SJC(28), PtGA, and PrGA;
 - Functional Assessment of Chronic Illness Therapy (FACIT)-Fatigue score
- Proportion of patients achieving at Week 2, Week 4, Week 8 and Week 12:
 - ACR20/50/70 response
 - Categorical DAS28-CRP response. Proportion of patients achieving categorical DAS28-CRP response will be measured as moderate/good European League Against Rheumatism (EULAR) response at each assessment time point;
 - Low Disease Activity (LDA) ($DAS28 \leq 3.2$)
 - DAS28-ESR remission ($DAS28 < 2.6$)
 - ACR/EULAR remission (TJC(28), SJC(28), CRP, and PtGA: all ≤ 1);
 - SDAI remission ($SDAI \leq 3.3$);
 - CDAI remission ($CDAI \leq 2.8$).
- Concentration of miR-124 expression in total blood (determined by qPCR) at baseline and week 8
- Change from Baseline in miR-124 expression in total blood at Week 8
- PK parameters:
 - Pre-dose plasma concentration of ABX464/N-Glu at Week 2 and Week 8;
 - Post-dose plasma concentration of ABX464/N-Glu at 1-, 2- and 3-hours post-dose at Baseline, Week 2 and Week 8;
 - Trough plasma concentration of ABX464/N-Glu at End of Study Visit
- The number of incidences of treatment-emergent serious adverse events;
- The number of incidences of treatment-emergent adverse events of special interest;
- The number of incidences of adverse events leading to investigational product discontinuation;
- The number of incidences of clinically significant laboratory abnormalities;
- The number of incidences of all AE (causally related and non-related) and SAE, further categorized by severity.

4.3 PHARMACOKINETIC VARIABLES

Pharmacokinetics will be measured via serum levels of plasma.

4.4 PHARMACODYNAMIC VARIABLES

No pharmacodynamic variables will be measured.

4.5 OTHER OUTCOME VARIABLES

Not applicable.

4.6 SAFETY VARIABLES

Safety will be evaluated by the following:

- Adverse events
- Laboratory parameters
- Vital signs (body temperature, weight, systolic and diastolic blood pressure, heart rate and respiratory rate)
- Physical examination
- ECG (PR, QRS, QT and QTc and Result: Normal, Abnormal NCS or Abnormal CS)

5 DEFINITIONS AND DERIVED VARIABLES

5.1 DEFINITIONS

Study Drug: Study drug is taken to mean either ABX464 or placebo.

Baseline: Baseline is defined by patient and by variable as the last non-missing value before the first dose of study drug

Study Day: Study day is the number of days since start of treatment where the date of first dose is counted as Day 0.

Treatment Exposure: Treatment exposure is the number of days during the treatment period that the patient was exposed to the study treatment and is calculated as:

$$(\text{Date_of_last_dose}) - (\text{Date_of_first_dose}) + 1$$

Compliance: Compliance is the number of doses actually taken divided by the scheduled number of doses expressed as a percentage.

Non-compliance: Non-compliance is defined as taking less than 80% or more than 120% of study medication.

Protocol Deviation: a deviation related to study inclusion or exclusion criteria, conduct of the trial, patient management or patient assessment. This refers to any change, divergence, or departure from the study design or procedures defined in the protocol. Deviations recorded by the Project Manager or CRA, or detected by Data Management or by Statistical programming checks as described in Section 6.3 will be identified and discussed at the Data Review Meeting before database lock to agree which should be included in Listing I6.2.2.

Screening and enrollment: Screening is the process of active evaluation of potential participants for enrollment in a trial. After a patient is recruited, screening occurs during the enrollment period to see if they meet the inclusion and exclusion criteria. If they meet the criteria, the subject is eligible to enroll in the trial.

Baseline and Screening failure: A patient is considered to be a baseline failure if the patient signs the informed consent but withdraws before the screening visit. A patient who does not fulfil the randomization criteria will be considered as a screening failure.

5.2 DERIVED VARIABLES

5.2.1 Disease Activity Score (DAS) 28-CRP (DAS28-CRP) and DAS28-ESR

The components of the DAS28 include:

- tender/painful joint count (TJC) (28),
- swollen joint count (SJC) (28),
- CRP (in mg/L) or ESR (in mm/h), and
- patient global assessment of disease (PtGA), expressed as a Visual Analog Scale (VAS) from 0 to 100 mm

They are calculated with the following formula:

$$\text{DAS28-CRP} = 0.56 \sqrt{\text{TJC28}} + 0.28 \sqrt{\text{SJC28}} + 0.36 \ln [\text{CRP}(\text{mg/L}) + 1] + 0.014 \text{PtGA}(\text{VAS}100\text{mm}) + 0.96$$

$$\text{DAS28-ESR} = 0.56 \sqrt{\text{TJC28}} + 0.28 \sqrt{\text{SJC28}} + 0.70 \ln [\text{ESR}(\text{mm/h})] + 0.014 \text{PtGA}(\text{VAS}100\text{mm})$$

5.2.2 Simplified Disease Activity Index (SDAI)

This composite index is defined by this equation:

$$\text{SDAI} = \text{TJC28} + \text{SJC28} + \text{PtGA} + \text{PrGA} + \text{CRP}$$

- PtGA is expressed as a VAS from 0 to 10 cm,
- Investigator global assessment of disease (PrGA) is expressed as a VAS from 0 to 10 cm, and
- CRP (mg/L).

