5.3.7. Disease parameters

• Laboratory disease parameters:

- The **acute phase reactants**, CRP and ESR, will be dosed at every visit.
- Blood samples (on gel tubes) for serum **cytokines** determination will be kept in the local laboratory, at -80°C (or -20°C if not possible), till the end of the study.
- Blood samples (on Truculture® tubes) for determination of **cytokines**, produced by immune cells after stimulation (incubation at 37°C for 24 hours), will be kept in the local laboratory, **at -20°C**, till the end of the study. These samples will be performed only where the incubation procedure is feasible.
- The blood samples for **flow cytometry cells count** (including at least B & T lymphocytes, myeloid cells and macrophages) will be kept in the local laboratory, at -80°C or will be processed immediately.

The processes for samples preparation, storage and shipment will be fully defined in the laboratory manual.

- **miR-124 modulation**

ABX464 up-regulates miR-124 in PBMCs, making this micro-RNA a potentially useful future biomarker for ABX464 treatment monitoring. Determination of miRNA level in total blood will be performed in order to assess treatment effect by comparing before and after treatment for this exploratory biomarker. Assays for miRNA determination (by qPCR method) will be conducted by a specialized central laboratory.

The total blood in Paxgene® tubes will be stored at -20°C according to lab manual instructions.

- **Disease Activity Score (DAS) 28-CRP (DAS28-CRP) and DAS28-ESR**

The components of the DAS28 include:

- tender/painful joint count (TJC) (28),
- swollen joint count (SJC) (28),
- CRP (in mg/L) or ESR (in mm/h), and
- patient global assessment of disease (PtGA), expressed as a Visual Analog Scale (VAS) from 0 to 100 mm

They are calculated with the following formula:

$$\text{DAS28-CRP} = 0.56 \sqrt{\text{TJC28}} + 0.28 \sqrt{\text{SJC28}} + 0.36 \ln [\text{CRP}(\text{mg/L}) + 1] + 0.014 \text{PtGA}(\text{VAS100mm}) + 0.96$$

$$\text{DAS28-ESR} = 0.56 \sqrt{\text{TJC28}} + 0.28 \sqrt{\text{SJC28}} + 0.70 \ln [\text{ESR}(\text{mm/h})] + 0.014 \text{PtGA}(\text{VAS100mm})$$

- **Simplified Disease Activity Index (SDAI)**

This other composite index is defined by this equation:

$$\text{SDAI} = \text{TJC28} + \text{SJC28} + \text{PtGA} + \text{PrGA} + \text{CRP}$$

- PtGA is expressed as a VAS from 0 to 10 cm,
- Investigator global assessment of disease (PrGA) is expressed as a VAS from 0 to 10 cm, and
- CRP (mg/L).

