- **Clinical Disease Activity Index (CDAI)**

This other composite index is defined by this equation (no acute phase reactant):

$$\text{CDAI} = \text{TJC28} + \text{SJC28} + \text{PtGA} + \text{PrGA}$$

- PtGA is expressed as a VAS from 0 to 10 cm,
- PrGA is expressed as a VAS from 0 to 10 cm.

- **Categorical DAS28-CRP response**

Proportion of patients achieving categorical DAS28-CRP response will be measured as moderate/good European League Against Rheumatism (EULAR) response.

The EULAR response criteria are defined as follows:

DAS28 improvement →	> 1.2	> 0.6 and ≤ 1.2	≤ 0.6
Present DAS28↓			
≤ 3.2	good response	moderate response	no response
> 3.2 and ≤ 5.1	moderate response	moderate response	no response
> 5.1	moderate response	no response	no response

- **DAS28-ESR remission**

A remission is considered when DAS28-ESR <2.6

- **Low Disease Activity (LDA)**

The limit to consider a Low Disease Activity (LDA) is: DAS28-ESR ≤ 3.2

- **SDAI remission**

The SDAI remission is considered achieved if the SDAI score ≤ 3.3

- **CDAI remission**

The CDAI remission is considered achieved if the CDAI score ≤ 2.8

- **ACR/EULAR remission:**

In 2011, the American College of Rheumatology (ACR) and EULAR decided to set new criteria to define RA remission.

Boolean-based criteria to be used for clinical trials are:

- Tender/painful Joint Count (28)
- Swollen Joint Count (28)
- CRP
- Patient Global assessment of disease (PtGA) [VAS scale 0 – 10cm]

All ≤ 1

- **Categorical ACR20/50/70 response**

The component of ACR assessment include:

- tender/painful joint count (28),
- swollen joint count (28),
- patient assessment of joint pain,
- Patient Global Assessment of Disease (PtGA)
- Physician's Global Assessment of Disease (PrGA),
- CRP and
- Disability index of the healthy assessment questionnaire (HAQ-DI).

Patient assessment of joint pain – VAS scale 0-10 cm

PtGA – Patient Global Assessment of disease activity [VAS scale 0 – 10cm]

PrGA – Physician Global Assessment of disease activity (VAS scale 0 – 10cm)

HAQ-DI: This patient reported outcome questionnaire is usually self-administered by the patient.

The following 8 categories are assessed by the HAQ-DI:

1. Dressing and grooming
2. Arising
3. Eating
4. Walking
5. Hygiene
6. Reach
7. Grip
8. Common daily activities

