3.2.1 Inclusion criteria

A patient will be eligible for inclusion in this study only if ALL of the following criteria apply:

- Men or women age 18 - 75 years;
- Patient with a confirmed and documented diagnosis of adult-onset rheumatoid arthritis, for at least 12 weeks, according to the revised 2010 ACR-EULAR classification criteria, including at least one positive criteria among the following: Rheumatoid Factor (RF), Anti-Citrullinated Peptide Antibody (ACPA) or bone erosion;
- Swollen joint count of ≥ 4 (28-joint count) and tender joint count ≥ 4 (28-joint count) at screening;
- Patient with a moderate to severe disease activity score DAS28 CRP of ≥ 3.2 and CRP ≥ 5 mg/L (≥ 4.76 nmol/L) at screening;

- Patient who had an inadequate response (IR), or failed either methotrexate (MTX) or/and anti-TNF α therapy (both administered for at least 12 weeks before IR) or were intolerant to anti-TNF α therapy.

In addition, MTX treatment should be given at a stable dose ≥ 10 mg/week (for at least 4 weeks prior to randomization). The maximal dose of methotrexate should not exceed a total of 20 mg/week. MTX treatment should be associated with folic acid at a dose ≥ 5 mg/week.

For the anti-TNF α therapy, the following wash-out period will be required:

- 30 days prior to randomization for adalimumab and etanercept
- 2 months prior to randomization for infliximab, certolizumab pegol, golimumab
- Patients with the following hematological and biochemical laboratory parameters obtained within 14 days prior to baseline:
 - Hemoglobin > 9.0 g dL $^{-1}$;
 - Absolute neutrophil count ≥ 1000 mm $^{-3}$;
 - Platelets $\geq 100,000$ mm $^{-3}$;
 - Total serum creatinine $\leq 1.3 \times$ ULN (upper limit of normal);
 - Creatinine clearance > 50 mL min $^{-1}$ by the Cockcroft-Gault equation within 60 days prior to baseline;
 - Total serum bilirubin $< 1.5 \times$ ULN;
 - Alkaline phosphatase, AST (SGOT) and ALT (SGPT) $< 1.5 \times$ ULN;
 - Negative screening for TB and HIV, HCV, HBV
- Patients are able and willing to comply with study visits and procedures as per protocol;
- Patients should understand, sign and date the written voluntary informed consent form at the screening visit prior to any protocol-specific procedures are performed;
- Patients should be affiliated to a social security regimen (for French sites only);

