5.2.3 Clinical Disease Activity Index (CDAI)

This composite index is defined by this equation (no acute phase reactant):

$$\text{CDAI} = \text{TJC28} + \text{SJC28} + \text{PtGA} + \text{PrGA}$$

- PtGA is expressed as a VAS from 0 to 10 cm,
- PrGA is expressed as a VAS from 0 to 10 cm.

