5.2.8 CDAI remission

The CDAI remission is considered achieved if the CDAI score ≤ 2.8.

5.2.9 ACR/EULAR remission:

In 2011, the American College of Rheumatology (ACR) and EULAR decided to set new criteria to define RA remission.

Boolean-based criteria to be used for clinical trials are:

- Tender/painful Joint Count (28)
- Swollen Joint Count (28)
- CRP
- Patient Global assessment of disease (PtGA) [VAS scale 0 – 10cm]

All ≤ 1.

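### SDAI adds CRP in mg/L with weight 1 against a remission limit of 3.3; the CRP unit that belongs to the formula and its limit should be confirmed before unblinding

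*SAP*

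**What the plan says.** **SDAI.** Protocol 5.3.7 and SAP 5.2.2 give the same equation: TJC28 + SJC28 + PtGA + PrGA + CRP, every coefficient 1. The protocol sets the scales with "Investigator global assessment of disease (PrGA) is expressed as a VAS from 0 to 10 cm, and", followed by CRP in mg/L. The SAP has the same text: "Investigator global assessment of disease (PrGA) is expressed as a VAS from 0 to 10 cm, and - CRP (mg/L".

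**CDAI.** SAP 5.2.3 drops CRP and keeps the other four terms: "This composite index is defined by this equation (no acute phase reactant").

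**Limits.** Protocol 5.3.7 has "The SDAI remission is considered achieved if the SDAI score" is 3.3 or less, and SAP 5.2.7 agrees. SAP 5.2.8 has "The CDAI remission is considered achieved if the CDAI score" is 2.8 or less, as does Protocol 5.3.7.

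**Boolean ACR/EULAR remission.** Protocol 5.3.7 introduces the list with "Boolean-based criteria to be used for clinical trials are" and requires both joint counts, CRP and PtGA all to be at most 1. PtGA has a scale (0–10 cm); CRP has no unit. SAP 5.2.9 is the same.

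**Entry.** SAP 3.2.1 and Protocol 4.2.1 require, at screening, "Patient with a moderate to severe disease activity score DAS28 CRP of" at least 3.2 together with CRP of at least 5 mg/L.

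**Use.** SDAI change, SDAI remission and Boolean remission at Weeks 2, 4, 8 and 12 are secondary endpoints (Protocol 2.4, SAP 4.2.2). SDAI change also goes into the mixed model in SAP 11.3.2.

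**The concern.** SDAI minus CDAI is CRP, and the two remission limits differ by only 0.5. If CRP is in mg/L, that gap leaves a patient at the CDAI limit half a milligram per litre, in a trial that screens for at least ten times as much. A gap that small would fit better if CRP entered on a scale ten times coarser.

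A second hint comes from the other indices. PtGA is on 0–100 mm in DAS28 and on 0–10 cm in SDAI, so one component was rescaled for SDAI. CRP keeps mg/L in both, although DAS28-CRP damps it through 0.36 × ln(CRP + 1) and SDAI adds it raw.

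If the limit was set for another unit, SDAI remission would be under-counted. If the formula itself was meant for another unit, SDAI change would give CRP ten times its intended weight. These are separate questions: the change score does not use the 3.3 limit.

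**Working it through.** The plan's figures here are definitions, so there is no derived figure to reproduce. The check applies the formula as written, then repeats it with CRP/10. That alternative is an assumption (1 mg/dL = 10 mg/L); neither document uses it.

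**Inputs.** SDAI = CDAI + CRP (SAP 5.2.2, 5.2.3). Limits 3.3 and 2.8 (SAP 5.2.7, 5.2.8). Screening minima TJC 4, SJC 4, CRP 5 mg/L (SAP 3.2.1).

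**1. CRP allowed for SDAI remission.** As written: 3.3 - CDAI. With CRP/10: 10 × (3.3 - CDAI).

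| CDAI | As written, mg/L | With CRP/10, mg/L |
|---|---|---|
| 0 | 3.3 | 33 |
| 1 | 2.3 | 23 |
| 2 | 1.3 | 13 |
| 2.8 | 0.5 | 5 |
| 3.3 | 0 | 0 |

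With every other component at zero, CRP 3.3 mg/L is remission, 3.4 is not, and 5 is over the limit by 1.7. At the CDAI limit the allowance is 3.3 - 2.8 = 0.5 mg/L, one tenth of the screening minimum. With CRP/10 it is 5 mg/L.

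**2. Fall in CRP needed when everything else is zero,** 1 - 3.3/CRP, as written:
- from 5 mg/L: 34%
- from 10 mg/L: 67%
- from 15 mg/L: 78%
- from 30 mg/L: 89%

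**3. SDAI change** = CDAI change + CRP change (or + CRP change/10). The pairs are illustrations, not data.

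| CDAI change | CRP change, mg/L | As written | With CRP/10 |
|---|---|---|---|
| -10 | -20 | -30 | -12 |
| -10 | +10 | 0 | -9 |
| -20 | -5 | -25 | -20.5 |

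In the third row CRP is 5/25 = 20% of the change as written.

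**4. CRP share of SDAI at the screening minima,** each global score g assumed between 0 and 10. As written, 5/(8 + 2g + 5): 5/13 = 38% at g = 0, 5/33 = 15% at g = 10. With CRP/10, 0.5/(8 + 2g + 0.5): 0.5/8.5 = 6%, 0.5/28.5 = 2%.

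**5. Boolean rule.** If the limit is 1 mg/L, the fall needed is 1 - 1/CRP: 80% from 5, 93% from 15, 97% from 30 mg/L. If it is 10 mg/L, it is 1 - 10/CRP: none from 5 or 10, 33% from 15, 67% from 30 mg/L.

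**The case against.** The strongest reply is that nothing in the documents contradicts mg/L. Protocol and SAP carry the same formula, unit and limit. Neither mentions mg/dL or CRP/10. A strict remission definition is a legitimate choice. This stands to the extent that no unit error can be declared from these texts. It does not settle the pairing: two copies of one definition do not validate it, Protocol 5.3.7 cites no source for the 3.3 limit, and SAP section 13 lists no references.

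Four stronger readings are tempting and are not supported.

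- *SDAI change is mostly CRP.* Not shown. In step 3 the CRP part can be 20% of the change, and in step 4 it can be 15% of the score. The 38% end needs both global scores at zero in a patient with four tender and four swollen joints.
- *The Boolean rule is a second numerical error.* It is a missing label. Where the efficacy text gives CRP a unit it is mg/L, for example "C-Reactive Protein (CRP) (mg/L") in SAP 4.2.1, and the shell of Listing 16.4.5.1 also has mg/L. A programmer would probably use mg/L. The Unit column in the biochemistry listing shell belongs to the laboratory data, not to the efficacy derivation.
- *All patients start at 5 mg/L or more.* The criterion applies at screening. Baseline may be up to 30 days later (Protocol 3.2), so the floor need not hold for change from baseline.
- *Disagreement between SDAI and CDAI remission proves the error.* The two can differ under either unit, because CDAI omits CRP. The unit decides how often.

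It is also fair that the consequence is limited. The same rule applies to all arms, no between-arm bias is shown, and CDAI, CRP and the other components are reported separately.

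**Conclusion.** The point holds as a unit check that should be made before unblinding. Followed exactly, the plan rules out SDAI remission for any CRP above 3.3 mg/L and allows 0.5 mg/L at the CDAI limit, against 33 and 5 mg/L if CRP/10 was meant. The same choice moves the illustrative SDAI change from 0 to -9. The 0.5-point gap between the two limits is evidence inside the documents that formula and limit may not share a CRP unit. It is not proof, because the source of the limit is not given.

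Confidence is high for the arithmetic and moderate for an actual unit error. The CRP/10 column is an assumption, as are the global scores in step 4 and the change pairs in step 3.

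Affected: SDAI change, SDAI remission and possibly Boolean remission, all descriptive secondary endpoints. Not affected: ACR20, DAS28, CDAI, the primary safety endpoint and power. This should be fixed, but it does not threaten the trial's main conclusions.

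**What to change.** Before unblinding, confirm from the source of the index which CRP unit belongs to the SDAI formula and to its 3.3 limit.

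- If mg/dL: enter CRP (mg/L)/10 in the SDAI equation in Protocol 5.3.7 and SAP 5.2.2.
- If mg/L: keep the equation and cite the source of the limit in both places.
- If it cannot be confirmed: report SDAI, its change and SDAI remission under both scalings, and say so in the SAP.

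In the same check, state the CRP unit for the Boolean rule wherever it appears, and rescale it if needed: Protocol Synopsis (Study Endpoints), Protocol 2.4 and 5.3.7, SAP 4.2.2 and 5.2.9. Leave DAS28-CRP in mg/L.

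The cost is one source check, at most one changed SDAI derivation line and one unit label for the Boolean rule, carried into both documents. Reporting both scalings would add a second version of the SDAI tables. No new data are needed, because Listing 16.4.5.1 already holds CRP in mg/L and the other components by patient and visit. SAP 1.1 says recruitment was still under way when the plan was written and that approval precedes unblinding, so the check fits the plan's own timetable. Changing a remission definition after unblinding would be hard to defend.

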5.2.3 Clinical Disease Activity Index (CDAI)

This composite index is defined by this equation (no acute phase reactant):

$$\text{CDAI} = \text{TJC28} + \text{SJC28} + \text{PtGA} + \text{PrGA}$$

- PtGA is expressed as a VAS from 0 to 10 cm,
- PrGA is expressed as a VAS from 0 to 10 cm.

5.2.4 Categorical DAS28-CRP response

Proportion of patients achieving categorical DAS28-CRP response will be measured as moderate/good European League Against Rheumatism (EULAR) response.

The EULAR response criteria are defined as follows:

DAS28 improvement →	> 1.2	> 0.6 and ≤ 1.2	≤ 0.6
Present DAS28↓			
≤ 3.2	good response	moderate response	no response
> 3.2 and ≤ 5.1	moderate response	moderate response	no response
> 5.1	moderate response	no response	no response

5.2.5 DAS28-ESR remission

A remission is considered when DAS28-ESR <2.6.

5.2.6 Low Disease Activity (LDA)

The limit to consider a Low Disease Activity (LDA) is: DAS28-ESR ≤ 3.2.

5.2.7 SDAI remission

The SDAI remission is considered achieved if the SDAI score ≤ 3.3.

5.2.8 CDAI remission

The CDAI remission is considered achieved if the CDAI score ≤ 2.8.

5.2.9 ACR/EULAR remission:

In 2011, the American College of Rheumatology (ACR) and EULAR decided to set new criteria to define RA remission.

Boolean-based criteria to be used for clinical trials are:

- Tender/painful Joint Count (28)
- Swollen Joint Count (28)
- CRP
- Patient Global assessment of disease (PtGA) [VAS scale 0 – 10cm]

All ≤ 1.

5.2.10 Categorical ACR20/50/70 response

The component of ACR assessment include:

- tender/painful joint count (28),
- swollen joint count (28),
- patient assessment of joint pain,
- Patient Global Assessment of Disease (PtGA)
- Physician's Global Assessment of Disease (PrGA),

- CRP and
- Disability index of the healthy assessment questionnaire (HAQ-DI).

Patient assessment of joint pain: VAS scale 0-10 cm.

PtGA: Patient Global Assessment of disease activity (VAS scale 0 – 10cm).

PrGA: Physician Global Assessment of disease activity (VAS scale 0 – 10cm).

HAQ-DI: This patient reported outcome questionnaire is usually self-administered by the patient.

The following 8 categories are assessed by the HAQ-DI:

1. Dressing and grooming
2. Arising
3. Eating
4. Walking
5. Hygiene
6. Reach
7. Grip
8. Common daily activities

The patients report the amount of difficulty they have in performing some of these activities. Each question asks on a scale ranging from 0 to 3 if the categories can be performed without any difficulty (scale 0) up to cannot be done at all (scale 3).

The highest score reported by the patient for any component question of the eight categories determines the score for that category. The sum of the computed categories scores is calculated and divided by the number of categories answered. This gives a total score in the 0 to 3 range.

Definition of the ACR20% response:

- $\geq 20\%$ improvement in tender joint counts
- $\geq 20\%$ improvement swollen joint counts
- $\geq 20\%$ improvement in 3 of the 5 remaining ACR core set measures:
 - PtGA,
 - PrGA,
 - patient assessment of joint pain,
 - HAQ-DI,

- CRP.

For ACR50% and ACR70%, an improvement of respectively 50 and 70% of the same parameters has to be observed.

5.2.11 Functional Assessment of Chronic Illness Therapy (FACIT)-Fatigue:

This questionnaire is a measure to assess the patient fatigue in chronic diseases, and is validated in RA. It includes 13 items.

The FACIT score calculation process is defined as follows:

FACIT-Fatigue Subscale Scoring Guidelines (Version 4) – Page 1

- Instructions:*
1. Record answers in "item response" column. If missing, mark with an X
 2. Perform reversals as indicated, and sum individual items to obtain a score.
 3. Multiply the sum of the item scores by the number of items in the subscale, then divide by the number of items answered. This produces the subscale score.
 4. **The higher the score, the better the QOL.**

Subscale	Item Code	Reverse item?	Item response	Item Score
FATIGUE SUBSCALE	HI7	4 -	_____	= _____
	HI12	4 -	_____	= _____
	An1	4 -	_____	= _____
	An2	4 -	_____	= _____
	An3	4 -	_____	= _____
	An4	4 -	_____	= _____
	An5	0 +	_____	= _____
	An7	0 +	_____	= _____
	An8	4 -	_____	= _____
	An12	4 -	_____	= _____
	An14	4 -	_____	= _____
	An15	4 -	_____	= _____
	An16	4 -	_____	= _____

Score range: 0-52

Sum individual item scores: _____
Multiply by 13: _____
Divide by number of items answered: _____ = **Fatigue Subscale score**

The FACIT scoring guide identifies those items that must be reversed before being added to obtain subscale totals. Negatively stated items are reversed by subtracting the response from “4”. After reversing proper items, all subscale items are summed to a total, which is the subscale score. For all FACIT scales and symptom indices, the higher the score the better the QOL.

Handling missing items: If there are missing items, subscale scores can be prorated. This is done by multiplying the sum of the subscale by the number of items in the subscale, then dividing by the number of items actually answered. This can be done on the scoring guide or by using the formula below:

$$\text{Prorated subscale score} = \text{Sum of item scores} \times \text{N of items in subscale} \div \text{N of items answered}$$

When there are missing data, prorating by subscale in this way is acceptable as long as more than 50% of the items were answered (e.g., a minimum of 4 of 7 items, 4 of 6 items, etc). The total score is then

calculated as the sum of the un-weighted subscale scores. In addition, a total score should only be calculated if ALL of the component subscales have valid scores.

